- d) A subject diary reminder call is a call approximately 2 days after vaccination
- e) Performed at End of Influenza Season but at least 180 days after last vaccination date
- f) Informed Consent Form can be collected before Study day 1
- g) Procedures that should be completed before vaccination
- h) Blood draws are only applicable for subjects randomized into the immunogenicity sub-set. Collect blood samples before vaccination
- i) ILI Symptom Assessment and Documentation Training includes use of ILI Booklet to be completed if an ILI occurs
- j) Performed until End of Influenza Season
- k) Subjects aged 6 through 11 months at enrollment will receive a dose of the MenC vaccine at study completion visit.  
\*Should an ILI be identified and a NP swab obtained, it is recommended to postpone the study completion visit, to allow for the ILI follow-up visit to occur (see Section 5.5, Study Completion)

**Table 1.2 Time and Events Table – Treatment and Follow-up Period for subjects with a previous influenza vaccination history (one dose regimen)**

Visit Type		Treatment Period			Follow-up Period	
		Clinic Visit a	Diary Reminder Call a	Clinic Visit a	Safety Follow-up Call a	Clinic Visit a,b,*
Study Day		1	V1 + 2 c	V1 + 28	V1 + 90	End of influenza season or 180 days after last vaccination d
Visit Number		V1		V2	V3	V4
Visit Window (Days)		n/a	-1/+1	0 to +7	0 to +7	0 to +14
Study Event	References					
Screening and Safety						
Informed Consent e	Section 5.1.1	√ e				
Review of Systems f	Section 5.1.2	√ f				
Medical History f	Section 5.1.2	√ f				
Demographic Information f	Section 5.1.2	√ f				
Physical Examination f	Sections 5.1.2 and 5.3.1	√ f		√ f		
Exclusion/Inclusion Criteria f	Section 4	√ f				
Influenza and MenC Vaccination History f	Section 5.1.2	√ f				√ f
Randomization f	Section 5.1.4	√ f				
Subject Diary Card Training	Section 5.2.1	√				
Subject Diary Card Reminder	Section 5.2.2		√			

		Treatment Period			Follow-up Period	

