Throughout the study, unscheduled visits are planned for subjects who manifest signs of influenza-like illness (ILI) during the influenza season and will be evaluated by testing of a, preferably, nasopharyngeal (NP) specimen for influenza (see [Section 5.2.5, ILI Symptom Assessment and Documentation Training](#)). A parent or LAR of the subject or a delegate is contacted weekly to capture these cases throughout the study, resulting in 30 to 45 ILI reminder calls.

The study has a treatment period and a follow-up period. For subjects with a previous influenza vaccination history, the treatment period begins at the time of vaccination and ends 28 days after vaccination and will consist of 2 clinical visits and one reminder call to complete the Subject diary card. The follow up period begins 28 days after vaccination and ends at the time of study completion visit. For subjects without or unknown previous influenza vaccination history, the treatment period begins at the time of first vaccination and ends 28 days after the second vaccination and will consist of 3 clinical visits and two reminder calls to complete the Subject diary card, one after each vaccination. The follow up period begins 28 days after second vaccination and ends at the time of study completion visit. All subjects, irrespective of previous influenza vaccination history, will receive 1 safety follow-up call 90 days after last vaccination during the follow up period and the follow-up period will conclude with a study completion visit (clinic visit or call).

All subjects aged 6 through 11 months at enrollment, irrespective of randomization to investigational or comparator group, will receive a dose of the MenC vaccine at the end of the study.

Safety data collection will include standard solicited adverse event reporting via subject diary card for 7 days after each study vaccine administration, all unsolicited AEs for 28 days after each vaccine administration, and special AE categories (SAEs, NOCDs, AEs leading to withdrawal, medically-attended AEs for 30 days after ILI onset) for the full duration of the study. In countries without a marketing authorization to use of *Neisvac-C* vaccine, safety (SAEs and NOCDs, and AEs leading to withdrawal) will be assessed 28 days after the MenC dose (given at Visit 5).

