### **Case Report Forms**

This study utilizes EDC system to collect study-related data from each subject. A trained healthcare professional is required to enter subject data in the eCRFs in English based on the (medical) information available in each subject's source record.

Data should be entered into the eCRF in a timely fashion following each subject's clinic visit, study procedure, or phone call. Each subject's eCRF may be compared with the subject's source records by an approved study monitor (or designee) over the duration of the study in order to ensure data collection accuracy.

The following additional rules apply to documentation of subject diary card information collected in the CRFs:

1. The site must enter all readable entries in the subject diary card into the eCRF, including those values that may be biologically implausible (e.g. body temperature: 400°C).
2. Any illegible or implausible data should be reviewed with the subject's parent(s)/LAR/delegate. If an underlying solicited or unsolicited adverse event is described on review with the subject, this should be described in the source document and reported as an unsolicited adverse event in the Adverse Event eCRF (e.g., if the subject above confirms body temperature of 40°C on the day in which body temperature: 400°C was written into his/her subject diary card, this fever of 40°C should be recorded in the Adverse Event eCRF).
3. Any newly described safety information (including a solicited adverse event) must not be written into the subject diary card and must be described in the study file as a verbally reported adverse event. Any adverse event reported in this fashion must be

described as an unsolicited adverse event and therefore entered on the Adverse Event eCRF.

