## **5.4 Procedure(s) related to Protocol Defined ILI episodes**

### **5.4.1 ILI Reminder Calls**

Active surveillance for per protocol defined ILI will be conducted weekly via a reminder call or during planned clinic visits, from Visit 1 until the end of the influenza season. The subject's parent(s)/LAR will be asked via a checklist to determine if symptoms of ILI are present. The purpose of the reminder call is to trigger an unscheduled visit and nasopharyngeal (NP) swab collection. During every reminder call, the subject's parent(s)/LAR will be instructed to report and visit the study site in case of an ILI episode as soon as possible (see [Section 5.4.2, Unscheduled Visit\(s\)](#)). The reminder calls are not intended to collect any clinical data. If during the ILI reminder call an ILI is identified, a visit to the study site should be planned as soon as possible, as described in [Section 5.4.2, Unscheduled Visit\(s\)](#). In countries, in the exceptional case where calls are not feasible, study site personnel may visit the subject's homes to inquire about signs and symptoms of illness in the subject.

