### **5.4.2 Unscheduled Visit(s)**

An unscheduled visit describes a non-routine study visit triggered by a specific event: (onset of) ILI symptoms during active ILI surveillance

Subject will be asked to come to the study site for an unscheduled visit within the first 24 hours or as soon as possible following ILI onset to ensure optimal viral yield. Preferably, samples will be accepted if collected up to 6 days following the day of ILI onset. In the exceptional case that a clinic visit is not feasible, a home visit may be considered.

The following procedures should be carried out during this unscheduled visit:

- a) The ILI symptoms and ILI Booklet will be reviewed and collected. The information should be mentioned in the subject's source documentation and recorded on the ILI event eCRF.
- b) Subjects meeting the protocol defined criteria for ILI will have a nasopharyngeal (NP) swab collected for evaluation for the presence of influenza virus. A NP swab is strongly preferred sampling method to ensure consistency across the study population (see Clinical Specimen Lab Manual for detailed procedures for collecting, processing and shipping ILI swab samples). NP swabs should be taken prior to antiviral therapy.

If an antiviral therapy has been given prior to swab sampling, this should be mentioned in the subject's source documentation and recorded on the Concomitant Medication page in eCRF. Subjects with ILI symptoms and its complications ought to be treated according to recent accepted (national) clinical standards.

- c) The Investigator will record the subjects body temperature as part of the Physical Examination (see [Section 5.1.2, Screening](#)).
- d) Physical examination findings will be recorded in the medical source documents and Adverse Events eCRF.
- e) The use of relevant medications and the occurrence of medically-attended AEs within 30 days after the onset of ILI episode will be assessed.
- f) ILI Symptom Assessment and Documentation Training including an ILI Booklet will be provided (see [Section 5.2.5, ILI Symptom Assessment and Documentation](#))

The site should schedule the ILI follow-up call with the subject's parent(s)/LAR.

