5.1 Time points and Visit Windows

Assessments required at each study visit is described in Schedule of Assessments ([Appendix A](#))

Day 1 is defined as the day of first dose of the vaccination.

Relative days after Day 1 are calculated as (assessment date – Day 1 date) + 1. Relative days prior to Day 1 are calculated as (assessment date – Day 1 date). The day prior to Day 1 is Day -1

All data will be analyzed using nominal study visits as defined in the Study Schedule see ([Appendix A](#)) and electronic case report form (eCRF).

Throughout the study, unscheduled visits are planned for subjects who manifest influenza-like illness (ILI) symptoms during the influenza season. The data collected at those visits will not be reallocated to one of the clinic visits, but rather the actual date will be listed.

(Protocol Table 1.3).

The following visit windows will be used.

Statistical Analysis Plan – Final v2.0

Sponsor Name: Seqirus UK Limited

Sponsor Protocol ID: V130_14

Table 2: Visit windows for subjects without or unknown previous influenza vaccination history (two dose regimen)

Study part	Scheduled visit	Time interval (days)
Treatment period	Clinic Visit V1	Day 1
	Diary Reminder Call	V1 + 2 Days (-1/+1 Day)
	Clinic Visit V2	V1 + 28 Days (+7 Days)
	Diary Reminder Call	V2 + 2 Days (-1/+1 Day)
	Clinic Visit V3	V2 + 28 Days (+7 Days)
Follow-up Period	Safety Follow-up Call V4	V2 + 90 Days (+7 Days)
	Clinic Visit V5	End of influenza season or V2 + 180 Days (+14 Days) (whichever is longer)
	Clinic Visit V6	V5 + 28 Days (+7 Days)

Table 3: Visit windows for subjects with a previous influenza vaccination history (one dose regimen)

Study part	Scheduled visit	Time interval (days)
Treatment period	Clinic Visit V1	Day 1
	Diary Reminder Call	V1 + 2 Days (-1/+1 Day)
	Clinic Visit V2	V1 + 28 Days (+7 Days)
Follow-up Period	Safety Follow-up Call V3	V1 + 90 Days (+7 Days)
	Clinic Visit V4	End of influenza season or V1 + 180 Days (+14 Days) (whichever is longer)

Visit window deviations will be reviewed prior to unblinding.

5.2 Missing Values – Missing Visits.

Missing, unused and spurious data will be dealt with as such. There is no intention to implement any procedure for replacing missing data.

Titer values recorded as <1:10 will be summarized as 1:5.

No imputation of missing solicited or unsolicited AEs will be used. The percentage of subjects with missing solicited AE assessments (e.g. missing Patient Diary) and

Statistical Analysis Plan – Final v2.0

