6.5 Efficacy

6.5.1 Primary Efficacy Endpoints Analysis

The primary efficacy analysis will be based on the FAS Efficacy. Eligible subjects for FAS analysis are subjects who are randomized and received at least one study vaccine and will be analyzed according to their randomized study vaccine (intent-to-treat analysis). Absolute vaccine efficacy will only be assessed for RT-PCR confirmed influenza episodes (primary efficacy endpoint 1a) and culture confirmed antigenically matched influenza episodes (primary efficacy endpoint 1b) with first onset of illness occurring at > 14 days after the last vaccination was administered in the treatment period until the end of the influenza season. Additionally, the primary objective will be evaluated in PPS Efficacy.

Time-to-event methodology based on a proportional hazard model will be used for all efficacy analyses to estimate the hazard ratio (HR). Absolute vaccine efficacy (aVE) against first occurrence RT-PCR confirmed influenza cases will be determined using a standard formula: $aVE = 1 - HR$ where HR is the hazard ratio for RT-PCR influenza confirmed cases in the QIVc group versus the comparator group. The HR will be estimated by a proportional hazards regression model, described below. For which the following null (H0) and alternative (H1) hypotheses will be tested:

$$H_0: 1 - HR \leq 0 \text{ versus } H_1: 1 - HR > 0$$

where HR is a hazard ratio of QIVc versus comparator and VE is vaccine efficacy. For both primary efficacy objectives, the HR and the related 97.5% CI of HR, for onset of first RT-PCR confirmed influenza will be estimated by a proportional hazards regression model with treatment effect as a fixed effect and stratifying covariates as random effect:

$$h_i(t|X) = h_0(t) \exp(\beta^T X + b^T Z),$$

with t denoting time to the influenza, β is the effect of treatment group indicated by X , b is random effect (assumed as a multivariable random gaussian variable with zero mean and diagonal covariance matrix), Z is random effect covariate (reflecting randomization strata).

Subjects that did not experience an event during observation period (be > 14 days after last vaccination up to end of influenza season) and subjects that dropped out from the study during observational period will be censored (right censoring) at the last available date in the eCRF prior to the end of influenza season.

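### SAP 6.5.1 does not make season end the censoring date for event-free children under surveillance throughout; if ILI call dates are not in the eCRF, a literal derivation biases VE toward 0

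*SAP*

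**What the plan says.** SAP 6.5.1 defines the observation period as more than 14 days after last vaccination up to season end. Children with no event in that period, and children who dropped out, "will be censored (right censoring) at the last available date in the eCRF prior to the end of influenza season". Protocol 8.4.2.2.3 says only that such children are right-censored. The model code in SAP Appendix B uses a time and a censoring variable without deriving either.

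The contacts that could supply a date are these:

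- **Completion contact.** Protocol Table 1.1, footnote e: "Performed at End of Influenza Season but at least 180 days after last vaccination date". SAP 5.1, Tables 2 and 3, take the later of the two dates.
- **Day-90 call.** Protocol 3.1: all children "will receive 1 safety follow-up call 90 days after last vaccination during the follow up period". The window is +7 days.
- **Weekly ILI reminder calls.** Protocol Table 1.1, footnote j: "Performed until End of Influenza Season". Protocol 5.4.1 adds: "The reminder calls are not intended to collect any clinical data".
- **General eCRF rule.** Protocol 3.4.2 asks for timely entry after each "clinic visit, study procedure, or phone call".
- **Event-driven entries.** ILI visits are "recorded on the ILI event eCRF" (Protocol 5.4.2). ILI follow-up calls (5.4.3), vaccinations (6.4) and the restricted adverse event categories of the follow-up period (7.1.2) can also leave dates.

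Season end is a fixed calendar date: end of May in the north, end of November in the south (Protocol List of Definitions; SAP 2.1).

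**The concern.** For a dropout the rule works, because the termination date is on the study completion eCRF page. For a child followed to the end, the completion contact is not before season end, so a literal derivation looks further back. Apart from the ILI calls, the last scheduled contact is then the day-90 (+7) call. Whatever lies between that call and season end depends on incidental entries.

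Cases are treated differently: they count until season end and stay in the risk set until onset. Late risk sets would therefore lose non-cases but keep every future case. The future cases are split between the arms in the ratio that the vaccine effect produces, so the fewer non-cases remain, the closer the late hazard ratio comes to 1.

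The sentence defines the time variable for both primary endpoints, for the secondary endpoints through the similar model in SAP 6.5.2, and for any interim test. Two competent programmers could build different datasets from it.

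**Working it through.** **1. The plan's own figures (SAP 2.3).** With one-sided alpha 0.0125, power 90% and 1:1 allocation, events = 4(2.2414 + 1.2816)² / (ln HR)².

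- 1a, HR 0.6: 49.64 / 0.2609 = 190.25, so 191. N = 190.25 / (0.08 × 1.6/2) = 2,973 (plan: 2,974).
- 1b, HR 0.5: 49.64 / 0.4805 = 103.33, so 104. N = 103.33 / (0.04 × 1.5/2) = 3,444 (plan: 3,446).

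The design is reproduced.

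**2. Assumptions that are not in the documents.** Season end is at day 180 after last vaccination. Of the comparator hazard, 20% to 60% falls after day 97. Later eCRF entries occur at random at a rate r per non-case child-month. The share of non-cases with a date after day 97 is 1 − exp(−r × 83/30.4): 74%, 49%, 24% and 13% for r = 0.50, 0.25, 0.10 and 0.05.

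**3. Hand check of the mechanism (1a, 60% of cases late).** Per arm of 1,487, the comparator has 1,487 × 0.08 = 119.0 cases and QIVc has 1,487 × 0.048 = 71.4. After day 97, 71.4 and 42.8 of these remain. Non-cases number 1,368.0 and 1,415.6. If a share p of non-cases is still at risk, the late hazard ratio is about 0.6 divided by (1,415.6p + 42.8)/(1,368.0p + 71.4).

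- p = 0.49: 0.6/0.993 = 0.604.
- p = 0.13: 0.6/0.910 = 0.659.
- p = 0: 0.6/0.6 = 1.

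The share p falls toward season end, but so does the number of future cases, so the day-97 ratio is a fair approximation. Weighting log HR 40% early (0.6) and 60% late gives VE of about 39.7%, 36.5% and 18.5%.

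**4. Simulation, endpoint 1a.** Single-covariate Cox model, two-sided 97.5% CI, N = 2,974, attack rate 8%, true VE 40%, 3,000 trials per cell. Monte Carlo error is about 0.2 VE points and 0.6 power points. Under the literal rule, non-cases are censored at the later of the day 90–97 call and the last incidental entry. Arrows run from 20% to 60% late hazard.

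| Censoring of non-cases | Non-cases with a date after day 97 | VE | Power |
|---|---|---|---|
| Season end | all | 40.1–40.2% | 89–90% |
| Last weekly call | all | 40.1–40.4% | 89–90% |
| Literal, r = 0.50 | 74% | 40.3 → 39.8% | 88–89% |
| Literal, r = 0.25 | 49% | 40.3 → 39.4% | 88–89% |
| Literal, r = 0.10 | 24% | 40.1 → 38.1% | 89 → 84% |
| Literal, r = 0.05 | 13% | 39.8 → 36.2% | 88 → 78% |

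With no later date for any non-case, VE is 34.5 → 19.7%. That is an unrealistic bound.

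**5. Variants.**

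- *10% dropout, 3,306 enrolled.* Season-end censoring of completers gives VE 39.9–40.2% and power 91%. The literal rule at r = 0.05 gives 39.8 → 37.4% and 90 → 83%.
- *1b (N = 3,446, true VE 50%).* Season end gives 50.4% and power 87–88%. The literal rule gives 50.4 → 49.9% (88%) at r = 0.25 and 50.4 → 48.7% (87 → 85%) at r = 0.05.
- *No vaccine effect.* Rejection is 0.97–1.30% against 1.25% nominal.
- *Second simulation.* Season end at day 195; 25%, 50% or 75% of hazard late; entries counted per child in total; error about 1 VE point. Weekly call dates give 1a VE 39.9–40.6%. A mean of 0.25 later entries (1 − e^−0.25 = 22% of non-cases with one) gives 39.1, 37.3 and 35.7%. A mean of 0.05 (5%) gives 37.2, 33.9 and 27.6%. Losses therefore grow further if later entries are rarer still.

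**The case against.** The harm needs call dates to be absent from an eCRF that is not among the documents, and several passages lean the other way. Protocol 3.4.2 asks for eCRF entry after phone calls and makes no exception for ILI calls. Protocol 3.8 makes four weeks without reply to these calls a trigger for lost-to-follow-up action, so sites must track them. The censoring sentence itself bounds the observation period at season end, so reading it as a cap is natural. All of this stands, but none of it makes the call date a stated eCRF field, and the sentence does not say that it is only a cap.

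Later entries may also be common. The ILI definition is broad, and each swabbed ILI schedules a follow-up call 30 to 37 days after onset. Rerunning 1a at 60% late hazard, with every entry treated as an ILI visit plus its call, moved VE from 36.1% to 37.7% and power from 76% to 82% at r = 0.05. At r = 0.10, VE moved from 38.2% to 39.0% and power from 84% to 87%. The low-rate losses shrink but do not vanish.

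A reader might infer from Protocol 5.4.1 that reminder calls leave no trace in the eCRF, so that nearly all non-cases are censored near day 97 and VE falls far below 40%. The documents do not support that. The sentence concerns clinical data, not contact dates, and several other entries can follow the day-90 call.

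**Conclusion.** The rule as written allows a derivation in which time at risk depends on outcome, and no other section supplies a season-end date for completers. This is a stated rule that can bias the hazard ratio toward 1, not merely missing detail. Whether it does so depends on two things the documents leave open: whether ILI call dates are eCRF fields, and whether the sentence is meant as a cap. If either is so, there is no material effect.

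Otherwise, under the assumed timing and entry rates, the 1a loss is under 1 VE point when about half of non-cases have a later entry. It is up to about 4 points, with power about 78%, when about 13% do. For 1b it is under 2 points over the same range. These are sensitivity figures: no document gives an entry rate.

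A reader might also infer that the rule favours the vaccine or threatens type I error. It does neither. The bias is conservative, and its cost is an understated VE and lost power. The change should be made, with medium confidence that it affects the result.

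**What to change.** Replace the censoring sentence in SAP 6.5.1 with a rule to this effect:

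- Event-free children under ILI surveillance through the season are censored at the protocol-defined season end. At an interim, they are censored at the earlier of data cut-off and season end.
- Children who withdrew, were lost to follow-up or moved to safety-only follow-up are censored at the last contact at which ILI status was ascertained, capped at season end. ILI call dates are used if held in the data. Otherwise the termination or consent-withdrawal date on the study completion eCRF page is used.

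A simpler rule, season end for anyone with a completion contact at or after it, would credit too much time. Protocol 3.8 lets children who withdraw continue for safety only, and others may be unreachable for weeks. At completion, Protocol 5.5 calls for a swab only if ILI onset was within the previous 6 days, and for none after season end, so earlier illness in these children would go untested.

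The cost is a short SAP edit before unblinding, plus a check of whether ILI call dates are in the data. Season end is already fixed, and the fallback dates are already collected. Study procedures do not change.

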6.5.2 Secondary Efficacy Endpoints Analysis

The analysis population for all secondary efficacy objectives will be based on the FAS Efficacy and repeated on the PPS Efficacy.

The secondary measure of efficacy is the estimate of absolute efficacy of QIVc versus a comparator to prevent moderate-to-severe RT-PCR influenza confirmed cases caused by any influenza Type A and/or Type B virus.

Moderate-to-severe ILI episode is defined as ILI episode complicated by one of the following:

- physician confirmed lower respiratory tract illness,
- physician confirmed acute otitis media, or hospitalization in the Intensive Care Unit (ICU),
- physician-diagnosed serious extra-pulmonary complication of influenza or supplemental oxygen requirement for more than 8 hours.

Secondary efficacy objectives are not associated with any hypothesis testing.

The model specification used to estimate absolute vaccine efficacy for the secondary objectives are similar to the model used for the primary efficacy endpoints.

Example SAS code is shown in [Appendix B](#).

